1.3 Risks and Benefits for Study Subjects

Recombinant erythropoietins (epoetin) have a relatively wide therapeutic window and are usually well tolerated provided that the stimulation of bone marrow is controlled by limiting the amount and rate of haemoglobin increase. The rate of haemoglobin increase may vary considerably between subjects and is dependent not only on the dose and dosing regimen of epoetin but also other factors, such as iron stores, baseline haemoglobin and endogenous erythropoietin levels, and the presence of concurrent medical conditions such as inflammation. In subjects with CKD, treatment of anaemia with r-HuEPO has improved cardiovascular function and the quality of life

to a greater extent. However, treatment with r-HuEPO to target haemoglobin concentrations of 13 g/dL or more (achieved mean concentrations >11 g/dL or 12 g/dL) has been consistently associated with high rates of cardiovascular disease, especially in subjects who are ESA-hypo responsive. Exaggerated pharmacodynamic response may result in hypertension and thrombotic complications. Moreover, PRCA due to neutralising anti-erythropoietin antibodies has been observed, predominantly in renal anaemia subjects treated with subcutaneously administered epoetin. Antibody-induced PRCA is a very rare event and usually takes months to years of epoetin treatment to develop. Clinical decision making should balance risks and benefits and usually favours r-HuEPO administration in subjects undergoing dialysis in whom haemoglobin concentrations are lower, quality of life is poorer, and transfusion is needed more often than for subjects with earlier stages of chronic kidney disease. ([17](#))

1.4 Route, Dosage, Dosage Regimen, Treatment Period

In this study EPIAO / EPREX will be administrated for a treatment period of 52 weeks, one to three times a week through IV route at the end of dialysis session. The dose will be adjusted individually to maintain haemoglobin at a level not exceeding 12 g/dl. The required dose will be calculated based on the haemoglobin.

Dosage adjustment: Refer section 5.1.7.

1.5 Compliance Statement, Ethics and Regulatory Compliance

This study will be conducted in compliance with the protocol, the ethical principles that have their origin in the Declaration of Helsinki, the International Council for Harmonization (ICH) consolidated Guideline E6 for Good Clinical Practice (GCP) (CPMP/ICH/135/95) and applicable regulatory requirement(s)

1.5.1 Subject Confidentiality

The Investigators and the Sponsor will preserve the confidentiality of all subjects taking part in the study, in accordance with GCP and local regulations.

The Investigator must ensure that the subject's anonymity is maintained. On the case report forms or other documents shared with Sponsor / Ecron Acunova (EA), subjects should be identified by a unique subject identifier as designated by EA. Documents that are not for submission to Sponsor / EA [e.g., signed Informed Consent Forms (ICF)] should be kept in strict confidence by the Investigator.

In compliance with ICH GCP guidelines, it is required that the Investigator and institution permit authorized representatives of the company, of the regulatory agency(s), and the Independent Ethics Committee (IEC) or Institutional Review Board (IRB) direct access to review the subject's original medical records for verification of study-related procedures and data. The Investigator is obligated to inform the subject that his/her study-related records will be reviewed by the above named representatives without violating the confidentiality of the subject.

1.5.2 Informed Consent Procedure

Before a subject's participation in the study, it is the investigator's responsibility to obtain freely given consent, in writing, from the subject or legally acceptable representative after adequate

explanation of the aims, methods, anticipated benefits, and potential hazards of the study and before any protocol-specific screening procedures or any study drugs are administered. The written ICF will be prepared in the local language(s) of the potential subject population.

In obtaining and documenting informed consent, the Investigator should comply with the applicable regulatory requirements, and should adhere to GCP and to the ethical principles that have their origin in the Declaration of Helsinki. The consent form and any revision(s) should be approved by the IEC or IRB prior to being provided to potential subjects.

The subject's written informed consent should be obtained prior to his/her participation in the study, and should be documented in the subject's medical records. The ICF should be signed and personally dated by the subject or a legally acceptable representative, and by the person who conducted the informed consent discussion (not necessarily the Investigator). The original signed ICF should be retained in accordance with institutional policy, and a copy of the signed consent form should be provided to the subject or legal representative. The date and time that informed consent was given should be recorded on the Case Report Form (CRF).

If the subject or legally acceptable representative cannot read, then according to ICH GCP Guideline, Section 4.8.9, an impartial witness should be present during the entire informed consent discussion. This witness should sign the ICF after the subject or the legally acceptable representative has orally consented to the subject's participation and, if possible, signed the ICF. By signing the ICF, the witness attests that the information in the ICF and any other written information was adequately explained to and apparently understood by the subject or the legally acceptable representative and that informed consent was freely given by the subject or the legally acceptable representative.

1.5.3 Regulatory Compliance

The study protocol, subject information and consent form, the investigator brochure or written instructions to be given to the subject, available safety information, subject recruitment procedures (eg, advertisements), information about payments and compensation available to the subjects and documentation evidencing the investigator's qualifications should be submitted to the IEC or IRB for ethical review and approval according to local regulations, prior to the study start. The written approval should identify all documents reviewed by name and version.

Changes in the conduct of the study or planned analysis will be documented in a protocol amendment and/or the Statistical Analysis Plan (SAP).

The investigator must submit and, where necessary, obtain approval from the IEC or IRB and/ or Sponsor for all subsequent protocol amendments and changes to the informed consent document or changes of the investigational site, facilities or personnel. The investigator should notify the IEC or IRB of deviations from the protocol and serious adverse events occurring at the site in accordance with local procedures.

2 STUDY OBJECTIVES AND HYPOTHESES

2.1 Study Objectives

2.1.1 Primary Objective

- To evaluate a 1:1 dose conversion from EPREX to EPIAO in term of clinical efficacy and safety in subjects with end-stage renal disease (CKD stage 5) receiving hemodialysis after IV administration.

2.1.2 Secondary Objectives

- To observe the frequency of adverse events following EPIAO and EPREX administration.
- To monitor the occurrence of anti-epoetin antibodies among subjects following at least 12 months of therapy

3 STUDY DESIGN

3.1 Overall Study Design

3.1.1 Study Type

This is a prospective, randomized, double blind, parallel group two arm study to evaluate a 1:1 dose conversion from EPREX to EPIAO in term of clinical efficacy and safety in subjects with end-stage renal disease (CKD stage 5) receiving hemodialysis.

Approximately 5 centers in Thailand and more than 8 centers in Russia will participate in the study.

[figure not shown]
[figure not shown]
3.1.2 Treatment Groups

The study population will consist of end stage renal disease (CKD stage 5) receiving haemodialysis. Subjects should be on a clinically stable haemodialysis for at least 3 months before screening. Approximately 5 centres in Thailand and more than 8 centers in Russia will participate in the trial. The eligible subjects will be treated with EPREX for a period of at least 3 months after screening (titration period) so as to randomize 264 subjects into the treatment period. The subjects with haemoglobin levels within the target range of 10 to 12.5 g/dl during the titration period will be randomly assigned in a 1:1 ratio to switch to treatment with EPIAO or continue treatment with EPREX. In substantiated cases a prolongation of the titration period is allowed up to maximum of 4 to 5 months on a case to case basis which will be considered as extended titration period. The assessment will be similar to the visit 7 (week 12/Day 84) if there is prolongation of the titration period. Thus, there will be a total of 2 treatment arms in the study.

1. Treatment arm A having 132 subjects will switch to an equivalent dose (to maintain the haemoglobin level) of EPIAO, one to three times a week, intravenously for period of 52 weeks at the end of dialysis session
2. Treatment arm B having 132 subjects will continue with the same dose of EPREX, one to three times a week, intravenously for period of 52 weeks at the end of dialysis session

Competitiveness of patient enrolment will be used. The recruitment will be stopped when the total enrolment of 264 subjects is achieved.

Figure 1: Schematic diagram of study design

3.1.3 Study Endpoints

Primary endpoint

- Mean absolute change in haemoglobin level from baseline to 6 months after treatment with EPIAO/EPREX in parallel groups (g/dl).

- Mean absolute change in weekly epoetin dosage per kg body weight from baseline to 6 months after treatment with EPIAO/EPREX in parallel groups (IU/kg/week).

Secondary endpoint:

- Proportion of subjects, hemoglobin values are within 10 - 12 g/dl for the last 4 weeks of the period for assessment of treatment efficacy and safety (Weeks 32-36)
- Proportion of subjects with any haemoglobin measurement outside the target range during the double-blind treatment period
- Mean hemoglobin and hematocrit levels every 4 weeks within treatment period (52 weeks)
- Mean doses of the study products (IU/kg/week) every 4 weeks throughout the study period (52 weeks)
- Incidence of blood transfusions

Safety endpoints:

- Incidence and nature of adverse events
- Incidence of drug related adverse events
- Clinically significant changes in the vital signs, physical and laboratory examination
- Number of subjects who prematurely withdrew from the study due to AE and SAE
- Number of subjects with presence of anti-erythropoietin antibodies (anti-EPO Ab)

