- The investigational product must be temporarily withheld until the result of immunogenicity assessments is shown negative, IP can be re-started upon confirmation of negative test for immunogenicity..

Fecal occult blood test

This test will be performed during screening visit as per PI discretion

Iron study

- Serum ferritin level
- Transferrin saturation (TSAT)
- Serum iron

- Total Iron Binding Capacity (TIBC) (optional)

These tests will be performed during screening, baseline visit (visit 8/Week 13/Day 91), visit 11 (week 16/Day 112), visit 13 (week 24/ Day 168), visit 16 (week 36/Day 252), visit 19 (week 48/Day 336) and visit 23 (week 64/ Day 448).

Intact parathyroid hormone level

This test will be performed during screening visit

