9.4 Efficacy Analyses

9.4.1 Primary Efficacy Analyses

- Mean absolute change in haemoglobin level from baseline to 6 months after treatment with EPIAO/EPREX in parallel groups (g/dl).
- Mean absolute change in weekly epoetin dosage per kg body weight from baseline to 6 months after treatment with EPIAO/EPREX in parallel groups (IU/kg/week).

The ANCOVA will be performed based on the normality of data for mean change between baseline to 6 months of EPIAO and EPREX with center, Hb level and weight as covariates. The 95% confidence intervals will be calculated for the treatment differences and is compared with pre-defined acceptance ranges: ± 0.5 g/dl for haemoglobin.

The ANCOVA will be performed based on the normality of data for mean change in weekly epoetin dosage per kg body weight baseline to 6-month treatment with EPIAO and EPREX with center, Hb level and weight as covariates. The 95% confidence intervals will be calculated for the treatment differences and is compared with pre-defined acceptance ranges: ± 45 IU/kg/week for dosage.

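### Cheap improvement: define the 6-month value of both co-primary endpoints as the mean over weeks 32-36, where haemoglobin and dose are already recorded, instead of leaving a point-to-point change

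*Protocol*

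**What the plan says.** Protocol Section 3.1.3 defines the co-primaries as "Mean absolute change in haemoglobin level from baseline to 6 months after treatment with EPIAO/EPREX in parallel groups (g/dl" and "Mean absolute change in weekly epoetin dosage per kg body weight from baseline to 6 months after treatment with EPIAO/EPREX". Section 9.4.1 repeats them and analyses each by ANCOVA "with center, Hb level and weight as covariates". It adds: "The 95% confidence intervals will be calculated for the treatment differences". These intervals are compared with "pre-defined acceptance ranges: ± 0.5 g/dl for haemoglobin" and "pre-defined acceptance ranges: ± 45 IU/kg/week for dosage".

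No section gives an averaging window for either co-primary.

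- **Start of the change.** Visit 8 is the visit labelled as baseline in Table 2 and in Section 8.5: "baseline visit (visit 8/Week 13/Day 91". For dose, Section 5.1.7 has one stable dose in IU/kg/week calculated and captured before treatment starts.
- **End of the change.** No visit is named as 6 months. Section 9.6 ties the equivalence analysis to 24 weeks of treatment and to Visit 16 (week 36). Section 3.1.5 runs the efficacy period to week 39.
- **Data available.** Section 7 has haemoglobin assessed at all scheduled visits and the epoetin dosage documented. Section 6.4 includes a blood count at Visit 15 (week 32) and Visit 16 (week 36).
- **A window already in use.** The first secondary endpoint in Section 3.1.3 is assessed "for the last 4 weeks of the period for assessment of treatment efficacy and safety (Weeks 32-36".

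**The concern.** A change between two single readings carries the visit-to-visit fluctuation of both. Haemoglobin varies between visits. Dose moves in steps of 2000 IU per week and is rounded up to a multiple of 2000 IU (Section 5.1.7), so the reading in one week can sit a full step away from the typical dose of that month.

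Both endpoints must succeed on a 95% interval lying inside the margin, so interval width is what the trial pays for. The protocol collects a second end-of-period reading and uses it for a secondary endpoint but, as worded, not for the co-primaries. Precision is also not in surplus: with the stated dropout of about 18%, 132 × 0.82 = 108 evaluable subjects per arm, slightly below the 112 in Section 9.8.

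**Working it through.** **Plan's own figure.** The 112 per arm cannot be reproduced, because no SD or assumed true difference is given. It can only be inverted. For two one-sided tests at 0.025 with true difference 0 and 80% power per endpoint, SD = margin × √(112/2) / (1.960 + 1.282):

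- Haemoglobin: 0.5 × 7.483 / 3.242 = 1.15 g/dl, giving a 95% half-width of 1.96 × 1.154 × √(2/112) = 0.30 g/dl.
- Dose: 45 × 7.483 / 3.242 = 103.9 IU/kg/week, giving a half-width of 1.96 × 103.9 × √(2/112) = 27.2 IU/kg/week.

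**Effect of averaging weeks 32 and 36.** Baseline stays at Visit 8 (week 13). Take unit variance at each visit, with r the correlation between weeks 32 and 36, and c32 and c36 their correlations with Visit 8. The residual variance after baseline adjustment is:

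- single visit (week 36): 1 − c36²
- mean of weeks 32 and 36: (1 + r)/2 − ((c32 + c36)/2)²

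The interval width changes by the square root of the ratio. All correlations below are assumptions.

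| Assumed structure | Width ratio, weeks 32 and 36 averaged |
|---|---|
| Equal correlation ρ, 0.2 to 0.9 | 0.76 to 0.86 |
| Subject effect + serial correlation + noise (three mixtures) | 0.87 to 0.89 |
| Serial only, 4-week correlation 0.5 to 0.95 | 0.87 to 0.94 |
| Dose as a random walk | 0.93 |

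Hand checks:

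- Equal correlation reduces to √[(1 + 2ρ)/(2(1 + ρ))]. At ρ = 0.2 this is √(1.4/2.4) = 0.764; at ρ = 0.9, √(2.8/3.8) = 0.858.
- Random-walk dose from week 13: the week 36 variance is proportional to 23, and that of the mean to (19 + 23 + 2 × 19)/4 = 20. So √(20/23) = 0.933, whatever the step size.

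The range is 0.764 to 0.938, a narrowing of about 6% to 24%. At the implied SD the haemoglobin half-width of 0.30 would become 0.28 (0.302 × 0.938) to 0.23 (0.302 × 0.764). The dose half-width of 27.2 would become about 25.4 (27.2 × 0.933).

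**A less favourable structure.** Suppose independent visit noise (SD 0.4-0.7 g/dl) plus a drift from baseline (SD 0.6-1.0 g/dl) that is identical at weeks 32 and 36. The unadjusted change variance is 2·sw² + sd² with a single end visit and 1.5·sw² + sd² with the end window.

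- sw = 0.6, sd = 0.8: √(1.18/1.36) = 0.93, 7% narrower.
- sw = 0.4, sd = 1.0: √(1.24/1.32) = 0.97, 3% narrower.
- sw = 0.7, sd = 0.6: √(1.095/1.34) = 0.90, 10% narrower.

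So 6% is not a guaranteed floor. The gain vanishes as the two end values become the same.

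**Averaging baseline as well.** Replacing Visit 8 by the mean of Visits 5-8, with the end value left single, gives ANCOVA width ratios of 0.81-0.97 (equal correlation), 0.97-0.99 (mixtures), 1.00-1.02 (serial only) and 1.00-1.025 (dose). It can help haemoglobin, but can also do nothing or slightly widen the interval.

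**Timing.** The mean of weeks 32 and 36 is week 34, which is 34 − 13 = 21 weeks after randomisation, against 23 weeks for Visit 16.

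**The case against.** The strongest objection is that the protocol nowhere states a single-visit derivation. It says only baseline and 6 months, Section 6.3 even speaks of baseline visits in the plural, and derivation rules are often left to a statistical analysis plan, which is not at hand. This stands in part: the single-visit reading is the natural one but is not explicit, so nothing here is a contradiction. It does not dispose of the point. The protocol sets a window in the endpoint list for a secondary endpoint and sets none for the co-primaries.

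Stronger readings that a reader might infer, and why they fail:

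- **Averaging four baseline and two end visits would cut the SD by 8-26%.** The arithmetic is right for an unadjusted change with independent visits: at sw = 0.6 and sd = 0.8, √1.36 = 1.17 falls to √0.91 = 0.95, or 18%. But the planned analysis adjusts for haemoglobin level, and serial correlation can remove the baseline part.
- **Baseline dose should be averaged too.** A stable dose is an entry condition (Section 4.1.2), and it is the dose converted 1:1. A mean over titration visits could differ from it.
- **A tolerated swing of 1.2 g/dl exceeds the ±0.5 margin.** The first limits one subject's change; the second bounds a difference between group means. They are not comparable.
- **Haemoglobin lags dose by two to ten weeks, so same-day values are mismatched.** Section 1 gives that interval for a clinically significant rise in anaemic subjects, not for maintenance. Averaging both over the same weeks would not remove a lag.
- **Withheld doses are noise.** Withholding above 13 g/dl is a real response to haemoglobin; averaging dilutes it but does not correct an error.
- **The change is free.** It needs no visit, but it moves the assessment earlier and redefines both co-primaries at a late amendment.

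**Conclusion.** The point holds as a cheap improvement. The data are collected, the window already exists in the protocol, and averaging weeks 32 and 36 narrowed the interval in every structure tried: roughly 6-24% under the tabulated correlation structures, with dose at about 7%, and 3-10% in the less favourable drift model. The direction is secure; the size is not, because the protocol states neither SD nor correlation.

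The documents do not support calling the endpoints wrong, biased or underpowered on this account. Nor do they support a firm gain from averaging baseline: it may add little for haemoglobin after adjustment and adds essentially nothing for dose.

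**What to change.** Amend Sections 3.1.3 and 9.4.1 before any unblinding, and so before the unblinded interim analysis in Section 9.6:

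- Define the 6-month value of each co-primary as the mean of haemoglobin, and of administered weekly dose in IU/kg/week, over weeks 32-36 (Visits 15 and 16). If one visit is missed, use the one available value; this is consistent with the rule in Section 9.2.1 against imputation.
- Keep baseline dose as the captured stable pre-switch dose. Name Visit 8 as baseline for haemoglobin, or, as an option, the mean of the last three titration visits and Visit 8.
- Report the single-visit change to Visit 16 as a sensitivity analysis.

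The cost is endpoint wording and a short derivation rule, with no new sample or visit. The drawbacks are an assessment centred about 2 weeks before Visit 16 and less averaging for subjects with one missed visit. A side benefit is that 6 months is at last tied to named visits.

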3.1.4 Duration of the Study

The duration of the subject participation will be for a maximum of 77 weeks.

3.1.5 Duration of Subject Participation

The duration of the subject participation will be of a maximum of 68 weeks, (77 weeks in case of extension of titration period) including 4 weeks of screening period, titration period of at least 3 months (maximum duration for 5 months), treatment duration of 26 weeks for efficacy and safety evaluation (weeks 13 through weeks 39) and treatment duration of 26 weeks for immunogenicity evaluation (weeks 40 through weeks 64). In substantiated cases a prolongation of the titration period is allowed up to maximum of 4 to 5 months on a case to case basis which will be considered as extended titration period. The assessment will be similar to the visit 7 (week 12/Day 84) if there is prolongation of the titration period.

3.1.6 Discontinuation Criteria

1. Subjects are free to drop out from the study at any time without stating any reason and they can choose not to receive the drug or equivalent after signing the consent. If the subject chooses not to receive the study drug after signing the consent, the subject must notify the Investigator before dispensing of the study drug. However, the subjects will continue to receive all the standard medical care, to which they are entitled.
2. Investigators may also, at their discretion, withdraw the subject from participating in the study at any time, with prior notification to the sponsor with the reason for the same.

However, subjects must be withdrawn from therapy, if any of the following events occur after giving the consent:

- a. Subject suffers from significant intercurrent illness or undergoes surgery during the course of the study where continued participation in the study presents a significant safety concern.
- b. Subject develops anti-epoetin antibodies or PRCA or severe allergic reaction
- c. Subjects requires epoetin dose more than 300 IU/kg/week
- d. Subject experiences adverse event or laboratory abnormality, when withdrawal would be in the best interest of the subject, as assessed by the investigator
- e. The subject fails to comply with the requirements of the protocol (e.g., visit window deviation) the subject may be withdrawn at the discretion of investigator and/or after discussion with medical monitor.
- f. It is necessary to further protect the health of the subject or the integrity of the study.
- g. Pregnancy.

3. The study is terminated by Sponsor, Regulatory Authorities or IEC/ IRB.

